7.1.1.2. Disease Progression

Participants who demonstrate radiologic or metabolic progression of disease as per the Lugano criteria will be considered as having met criteria for disease progression. The EOT visit should be performed as soon as possible, and the participant should continue with the safety and

survival follow-up periods of the study. Any new anticancer therapy (and associated response outcomes) should be captured in the eCRFs.

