8.8. End of Treatment and/or Early Treatment Discontinuation

The EOT visit will be performed at the time the decision is made to discontinue study treatment or after the participant has completed the prescribed treatment regimen (Cycle 12 Day 28). If the EOT visit coincides with a regular study visit, the EOT evaluations will supersede those of that scheduled visit, and the data should be entered in the EOT visit in the eCRF. The participant should be encouraged to return for the follow-up visits.

See Table 3 and Table 4 for the list of assessments be performed at the EOT visit.

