1. INTRODUCTION

Study INCMOR 0208-301 is a Phase 3, randomized, double-blind, placebo-controlled, multicenter study designed to investigate whether tafasitamab and lenalidomide as an add-on to rituximab provides improved clinical benefit compared with placebo and lenalidomide as an add-on to rituximab in participants with an INV-assessed diagnosis of R/R FL Grade 1 to 3a or R/R MZL who have been previously treated with at least 1 anti-CD20 antibody containing therapy (eg, rituximab, obinutuzumab). The primary endpoint is PFS by INV assessment in the FL population. The 3 key secondary endpoints are PFS by INV assessment in the overall population (FL and MZL populations), PET-CR rate at EOT by INV assessment in the FL population, and OS in the FL population.

The study consists of the screening period (\leq 28 days), treatment period (up to twelve 28-day cycles, with rituximab administered up to 5 cycles), and a 5-year follow-up period.

Approximately 528 participants with R/R FL and 60 to 90 participants with R/R MZL will be randomized at a 1:1 ratio to 1 of the 2 treatment groups. Stratified randomization will be performed separately for FL and MZL.

An interim analysis for futility will be performed at approximately 20% information rate (35 PFS events approximately) in the FL population (an HR of \geq 1.05 will be considered as a nonbinding futility boundary).

An IDMC will be established to monitor data, to ensure the safety of the participants enrolled in this study, and to evaluate the efficacy of the treatment during planned interim analysis. Details of the IDMC review are defined in a separate IDMC charter.

The purpose of this SAP is to provide details of the statistical analyses that have been outlined in the INCMOR 0208-301 Protocol.

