5.3. Analysis Populations

A full description of the populations for analysis is presented in Table 4.

Table 4: Analysis Populations

Population	Description
All screened	All participants who sign the ICF.
FAS	All randomized participants. Treatment groups for this population will be determined according to the treatment they were assigned at the time of randomization.
	The FAS will be used for the summary of demographics, baseline characteristics, participant disposition, and analyses of all efficacy data.
PPS	The subset of the participants in the FAS who are compliant with the requirements of the clinical study Protocol with no important Protocol deviations. All important protocol deviations or conditions leading to exclusion from the PPS will be detailed in the Protocol Deviation Specifications and identified prior to database lock for the primary analysis. Sensitivity analyses of the primary endpoint may be performed using the PPS.
MRD blood-evaluable set	All participants in the FAS who received at least 1 dose of tafasitamab/placebo, lenalidomide, or rituximab with identifiable clonality in blood sample at Cycle 1 Day1.
MRD bone marrow-evaluable set	All participants in the FAS who received at least 1 dose of tafasitamab/placebo, lenalidomide, or rituximab with either identifiable clonality in bone marrow at screening or identifiable clonality in blood sample at Cycle 1 Day 1.
SAF	All randomized participants who received at least 1 dose of tafasitamab/placebo, lenalidomide, or rituximab. Treatment groups for this population will be determined according to the actual treatment the participant received regardless of assigned treatment at the time of randomization. All safety analyses will be conducted using the SAF.
FDG-avid population	All randomized participants with a PET scan at baseline with a resulting Deauville score of 4 or 5.

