7.3. Analysis of the Primary and Key Secondary Efficacy Endpoints

7.3.1. Primary Efficacy Analysis for Progression-Free Survival in Follicular Lymphoma

Progression-free survival by INV assessment is defined as the time from the date of randomization to the date of first documented disease progression, as determined by disease assessment per the Lugano classification (Cheson et al 2014) or death due to any cause, whichever occurs earlier. For the primary analysis, PFS will be censored if no PFS event is observed before the cutoff date or the date that a new antilymphoma therapy is started. Censoring for PFS will follow the algorithm outlined in Table 6, which is based on the FDA Guidance (FDA 2015, FDA 2018).

Table 6: Evaluation and Censoring of Progression-Free Survival

Situation	Date of Progression or Censoring	Outcome	Censoring Reason
No baseline tumor assessments	Date of randomization	Censored	No baseline assessment
No valid postbaseline response assessments	Date of randomization	Censored	No postbaseline assessment
Progression documented between scheduled response assessments	Date of first overall response of PD	Progressed	Not applicable
No progression	Date of last adequate tumor assessment (not NE and not missing) prior to cutoff date	Censored	Ongoing
Study discontinuation without documented progression	Date of last adequate tumor assessment (not NE and not missing) prior to cutoff date	Censored	Study discontinuation
New antilymphoma treatment started	Date of last adequate tumor assessment with no documented progression (not NE and not missing) on/before starting a new antilymphoma treatment	Censored	Start of new antilymphoma treatment
Death before first progressive response assessment	Date of death	Progressed	Not applicable
Death between adequate response assessments	Date of death	Progressed	Not applicable
Death or progression after 2 or more missed assessments	Date of last progression assessment with documented nonprogression	Censored	Death or PD after 2 or more missed assessments

The date of last adequate tumor assessment is the date of the last tumor assessment with an overall lesion response of CR, PR, or SD. In this case, the last tumor evaluation date at that assessment is used. If a PFS event is observed after a single missing or nonadequate tumor assessment, the actual date of event will be used, as per the Lugano classification (Cheson et al 2014).

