3.4.3.x	Summary of Pulse	SAF	X	X	X			X
3.4.4.x	Summary of Respiratory Rate	SAF	X	X	X			X
3.4.5.x	Summary of Body Temperature	SAF	X	X	X			X
3.4.6.x	Summary of Weight	SAF	X	X	X			X

Figures

In the figure number the .x will specify the subset of participant included:

- .1: FL
- .2: MZL
- .3: Overall
- .4: Overall Japanese Population

Figure No.	Title	Pop	FL	MZL	Overall	Jap Overall
4.1.x	Kaplan-Meier Estimates of Progression-Free Survival	FAS	X	X	X	X
4.2.x	Kaplan-Meier Estimates of Overall Survival	FAS	X	X	X	X
4.3.x	Kaplan-Meier Estimates of Duration of Response	FAS	X	X	X	X
4.7.x	Kaplan-Meier Estimates of Progression-Free Survival on Next Treatment	FAS	X	X	X	Х
4.8.2.x	Kaplan-Meier Estimates of Progression-Free Survival by Number of Prior Lines	FAS	X	X	X	X
4.8.4.x	Kaplan-Meier Estimates of Progression-Free Survival by Refractoriness to Anti-CD20	FAS	X		X	X
4.8.5.x	Kaplan-Meier Estimates of Progression-Free Survival by CR at End of Treatment	FAS	X		X	X
4.8.6.x	Kaplan-Meier Estimates of Progression-Free Survival by MRD Status at End of Treatment	FAS	X		X	X
4.9.1.x	Line Graph of B-cell Counts Across Visits	FAS	X	X	X	X
4.9.2.x	Line Graph of Neutrophils Cell Counts Across Visits	FAS	X	X	X	X
4.9.3.x	Line Graph of Platelets Cell Counts Across Visits	FAS	X	X	X	X
4.9.5.x	Line Graph of IgG Across Visits	FAS	X	X	X	X
4.9.6.x	Line Graph of IgA Across Visits	FAS	X	X	X	X
4.9.7.x	Line Graph of IgM Across Visits	FAS	X	X	X	X

Listings

In the listing number the .x will specify the subset of participant included:

- 1: Overall Population
- 2: Overall Japanese Population

Listing No.	Title	Population	Overall	Japanese Overall
2.1.1.x	Participant Enrollment and Disposition Status	FAS	X	X
2.1.2.x	Participant Inclusion and Exclusion Criteria Violations	Screen Failed	X	X
2.2.1.x	Protocol Deviations	FAS	X	X
2.3.1.x	Analysis Population	FAS	X	X
2.4.1.x	Demographic and Baseline Characteristics	FAS	X	X
2.4.2.x	Baseline Disease Characteristics and Disease History	FAS	X	X
2.4.3.x	Prior Radiation Treatment	FAS	X	X
2.4.4.x	Prior Therapy	FAS	X	X
2.4.5.x	Prior Surgery or Surgical Procedure	FAS	X	X
2.4.6.x	Medical History	FAS	X	X
2.4.7.x	Prior and Concomitant Medication	FAS	X	X
2.4.8.x	Premedication Given Prior to Tafasitamab/Placebo Administration to Mitigate Potential Infusion-Related Reactions	FAS	X	X
2.4.9.x	Stratification Factors IRT versus eCRF	FAS	X	X
2.5.1.x	Study Drug Information - Tafasitamab	SAF	X	X
2.5.2.x	Study Drug Administration - Tafasitamab	SAF	X	X

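### Figures 4.8.5 and 4.8.6 group PFS by CR or MRD status at end of treatment in the FAS with no landmark visible: this biases the CR figure and can bias the MRD figure

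*SAP*

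**What the plan says.** SAP Appendix A lists two Kaplan-Meier figures whose groups are fixed at EOT: Figure 4.8.5, "Kaplan-Meier Estimates of Progression-Free Survival by CR at End of Treatment", and Figure 4.8.6, "Kaplan-Meier Estimates of Progression-Free Survival by MRD Status at End of Treatment". The population column reads FAS for both. They sit in one series with Figures 4.8.2 and 4.8.4, which group by baseline factors (prior lines, refractoriness to anti-CD20).

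SAP Section 5.3 describes the FAS as "All randomized participants. Treatment groups for this population will be determined according to the treatment they were assigned at the time of randomization". The one PFS definition in the readable SAP, Section 7.3.1, is: "Progression-free survival by INV assessment is defined as the time from the date of randomization to the date of first documented disease progression", or death if earlier.

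EOT is not a fixed time. Protocol Section 8.8 says "The EOT visit will be performed at the time the decision is made to discontinue study treatment", or at Cycle 12 Day 28 for those who complete treatment. After progression, Protocol Section 7.1.1.2 says "The EOT visit should be performed as soon as possible".

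For the MRD rate endpoint, SAP Section 7.4.2 uses peripheral blood at EOT in the MRD-blood evaluable set, and counts a participant without a postbaseline result as not negative. No rule is given for Figure 4.8.6.

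The figure titles state no time origin. The readable text contains no landmark, no time-dependent covariate and no restriction to participants event-free at EOT. Section 10.1 cites a Section 7.5.4, but Section 7.5 is not in the public text, and the sample displays are held separately.

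**The concern.** A group label that becomes known only at EOT is applied to survival time counted from randomization. A participant in CR at EOT has, by construction, passed through the whole treatment period without progression or death. One who progresses or dies during that period cannot be in CR at EOT and lands in the other group. The CR curve is therefore flat up to EOT and the non-CR curve carries all the early events, whether or not CR has any bearing on what follows.

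At stake is the reading of two displays that invite a prognostic interpretation: that reaching CR or MRD negativity at EOT goes with longer PFS. On the layout as listed, Figure 4.8.5 would appear to show this even if it were false.

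**Working it through.** **Inputs from SAP Section 3.3 and Table 2.** Median PFS 42.8 months (TGA) and 27.8 months (TGB), HR 0.65, 174 events, 448 participants before dropout, 15% dropout, 528 randomized, 21 months of enrollment, 12 months of follow-up. Treatment lasts up to twelve 28-day cycles.

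**The plan's own figures first.** The two figures carry no stated number, so this only confirms that the design inputs are read correctly.
- Events (Freedman, 1:1, 2-sided 5%, 80% power): (1.960 + 0.842)² × (1.65/0.35)² = 174.4, against 174 stated.
- Randomized: 448/(1 − 0.15) = 527.1, rounded up to 528, as stated.

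**Step 1, timing of EOT for completers.** 12 × 28 = 336 days; 336/30.4375 = 11.04 months.

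**Step 2, PFS events before day 336** (exponential PFS, from randomization).
- TGA: 1 − exp(−ln 2 × 11.04/42.8) = 16.4%, about 43 of 264.
- TGB: 1 − exp(−ln 2 × 11.04/27.8) = 24.1%, about 64 of 264.
- Pooled: 20.2%, about 107 of 528.

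**Step 3, make-up of the groups in Figure 4.8.5.** Let g be the share in CR among those event-free at EOT (an assumption; the documents give none). The share of the non-CR group with an event before EOT is 0.202/[0.202 + 0.798 × (1 − g)]. The share in the CR group is zero.

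**Step 4, size of the spurious separation.** 500 simulated trials per scenario, n = 528, uniform 21-month accrual, cutoff at 33 months, about 15% dropout. CR was assigned at random among those still followed and event-free at day 336, so the true association is nil. Everyone else, including dropouts before day 336, was placed in the non-CR group. Unadjusted Cox model, HR as non-CR over CR.

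| g | Non-CR group with event before EOT | 24-month PFS, CR vs non-CR | HR from randomization | HR from day-336 landmark |
|---|---|---|---|---|
| 30% | 27% | 77% vs 57% | 2.7 | 1.01 |
| 50% | 34% | 77% vs 52% | 3.3 | 1.01 |
| 70% | 46% | 77% vs 43% | 4.5 | 1.00 |

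The HR from randomization reached nominal p < 0.05 in every simulated trial; from the landmark it did so in 4% to 8%. The SAP attaches no test to these figures, so the p-value only shows that the separation is far beyond noise. A smaller separate run (80 trials per scenario, Cox model stratified by arm, cutoff 33.5 months) gave HRs of CR over non-CR of 0.39, 0.33 and 0.23. Their reciprocals are 2.6, 3.0 and 4.3, and the landmark HRs were 0.98 to 1.04.

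**Step 5, Figure 4.8.6.** The group of an early leaver depends on the EOT blood sample and on the rule for missing samples. Assume 50% MRD-negative among those event-free at day 336, and vary the share of participants leaving before day 336 who are classed as MRD-negative:

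| Early leavers classed MRD-negative | HR, non-negative over negative |
|---|---|
| 0% | 3.3 |
| 10% | 2.4 |
| 25% | 1.7 |
| 50% | 0.99 |

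The effect vanishes at 50% because the negative share is then the same in early leavers and in the rest, so the grouping carries no information about event time.

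**The case against.** The strongest reply is that the visible specification of each figure is a title and a population label, and the section and shells that would define it are not public. Text withheld from publication cannot be counted as missing. Nor does the FAS label settle the matter. Figure 4.3 and Table 2.2.11, on duration of response, are also listed as FAS, yet Section 7.4.4 limits that endpoint to responders and starts it at first response. The column may simply name the parent set, and Appendix A calls its lists guidelines. This stands: a reader might infer that the SAP rules out a landmark, and the documents do not support that.

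A second reply also stands. A reader might infer that early progressors are MRD-positive by definition, as they are non-CR by definition. They are not. Their EOT visit follows progression, and a blood sample taken then can be negative. The Section 7.4.2 rule for missing results is written for the rate endpoint in the evaluable set and is not stated to carry over.

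Third, the figures are descriptive. The readable SAP attaches no HR or test to them, they are outside the hierarchy in Section 3.2, and no document says that they will support a prognostic claim. This stands too.

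What remains is that the readable text, followed as written, produces a biased CR figure, and nothing in that text prevents it.

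**Conclusion.** The point holds conditionally. If Figure 4.8.5 is drawn from randomization in the FAS, guarantee-time bias is structural, with a spurious HR of about 2.7 to 4.5 where the true value is 1. If Figure 4.8.6 is drawn the same way, the spurious HR lies between about 3.3 and about 1.0, according to a classification rule that the readable SAP does not give.

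These sizes rest on exponential PFS at the SAP medians, EOT at day 336 for everyone event-free and in follow-up then, 30% to 70% in CR (50% MRD-negative for Figure 4.8.6), and status unrelated to later PFS. The status proportions and the share of early leavers who are MRD-negative are assumptions, not document figures.

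The documents do not support two further steps that a reader might take: that the trial's conclusions are at risk, since the primary test and the hierarchy are unaffected; or that no landmark exists anywhere in the plan, since Section 7.5 and the shells cannot be seen. It is still worth correcting, because the remedy is cheap and the display as listed could mislead.

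**What to change.** Unless Section 7.5 or the shells already do this, define both figures as landmark displays and make Appendix A say so.

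- **Landmark time.** Use a fixed time after the planned EOT assessment and its window. A cut at exactly 48 weeks from randomization would lose or misclassify completers: EOT is counted from C1D1, treatment should start within 3 days of randomization (Protocol Section 8.1.2), the EOT visit has a ±2-day window (Table 3) and Year 1 scans have ±2 weeks (Section 8.2.4). Day 336 from C1D1 plus 14 days gives day 350, at most 353 days from randomization. That is inside the planned 12-month minimum follow-up (12 × 30.4375 = 365 days).
- **Who is included.** Only participants event-free and under follow-up at the landmark, classified by EOT status known by then, with the clock starting at the landmark.
- **Figure 4.8.6.** Restrict it to the MRD-blood evaluable set and state how missing or unevaluable EOT samples are handled.
- **Labels.** Replace FAS in the population column with the landmark set. Any HR quoted beside the figures should come from that set.

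The cost is a few sentences in the SAP and minor reprogramming of two figures. The downside is that participants with events before the landmark are not plotted. Under the SAP medians, events by day 350 (11.50 months) would be 17.0% in TGA and 24.9% in TGB, or 264 × (0.170 + 0.249) = about 111 of 528. The footnote should report the number excluded by arm.
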